3.3 Completeness of follow-up

The number and percentage of participants with follow-up information at day 28 after randomisation will be reported.

3.4 Adherence to treatment

The number and proportion of patients who did not receive the treatment they were allocated will be reported, as well as details of the number of days of treatment received.

4 COMPARATIVE ANALYSES

For all outcomes, pairwise comparisons will be made between the tecovirimat and placebo arms performed on the ITT population at 28 days after randomisation.

4.1 Outcomes

4.1.1 *Primary outcome*

The primary outcome is defined as the first day on which all skin lesions are scabbed or desquamated and mucosal lesions healed, up to 28 days after randomisation (regardless of whether active, unscabbed, lesions are reported on subsequent days). Missing values for a particular day will be imputed as the reported value taken nearest in time before or afterwards (counted in whole days; in the event of a tie the reported value taken beforehand will be used).

For time-to-event analyses of this outcome, the tecovirimat group will be compared with the placebo group using a stratified log-rank test (days since symptom onset ≤ 7 and >7 days). Kaplan-Meier estimates for the time to event will also be plotted, with associated log-rank p-values. The log-rank 'observed minus expected' statistic (and its variance) will also be used to estimate the average event rate ratio (and its confidence interval) for those allocated to tecovirimat vs placebo.

4.1.2 *Secondary outcomes*

Secondary outcome (i) is defined as the first day on which all skin lesions are completely resolved, meaning all scabs have dropped off with intact skin remaining underneath, and mucosal lesions have healed, up to 28 days after randomisation (regardless of whether unhealed lesions are reported on subsequent days). Imputation of missing data and the method of time-to-event analysis will be as for the primary outcome above.

The remaining secondary outcomes are defined as the time to consistently negative culture for monkeypox virus in serial self-collected swabs, either taken from the throat (secondary outcome (ii)), or the most recent active skin or mucosal lesion (secondary outcome (iii)). These swabs are collected on days 7, 14, 21, and 28 after randomisation, and will be analysed using an interval censored Weibull model. A negative culture will be considered 'consistently negative' if it is not followed by a positive culture on the same type of swab during subsequent assessments.

4.1.3 *Subsidiary outcomes*

Clinical status on an ordinal scale will be compared between tecovirimat and placebo groups using a proportional odds model.⁶ Howard's method will be used if the proportional odds assumption is not satisfied.⁷ Monkeypox virus DNA concentration will be compared between groups using the Wilcoxon rank-sum test.

Time to sustained absence of use of analgesia for monkeypox symptoms is defined as the first day from which analgesia is consistently not required until day 28. Imputation of missing data and the method of time-to-event analysis will be as for the primary outcome above.

4.1.4 *Safety outcomes*

The number and percentage of patients suffering suspected serious adverse reactions, suspected unexpected serious adverse reactions, and death (overall and by cause), will be listed by trial allocation. Adverse events of special interest (listed in 2.6.4) and reasons for study drug discontinuation, will be presented by randomised group as counts and percentages. Where possible, the absolute risk differences will be presented with confidence intervals, analysed using Fisher's exact test.

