**Placebo-controlled randomised trial of tecovirimat
in non-hospitalised Mpox patients (PLATINUM)**

Background: Mpox is an acute febrile rash illness caused by the monkeypox virus. Since its first human identification in 1970, the majority of cases have been reported from Africa. Historically, there have been sporadic travel associated cases in countries outside of Africa, with very limited onward transmission.

Following notification from the United Kingdom to WHO on the 15th of May 2022, of two confirmed and one probable case of mpox, person-to-person transmission of mpox has been observed in multiple countries outside of Africa.

Several investigational antivirals demonstrate activity against monkeypox virus in vitro and in animal models, but none has been evaluated in a clinical trial. The most promising is tecovirimat, which is an oral anti-viral drug developed by SIGA Technologies, Inc. and approved by the US Food and Drug Administration (FDA) for the treatment of smallpox and by the European Medicines Agency (EMA) and Medicines and Healthcare products Regulatory Agency (MHRA), under an exceptional circumstances rule, for the treatment of smallpox, cowpox and mpox.

Eligibility and randomisation: This protocol describes a double-blind, placebo-controlled, randomised trial among non-hospitalised adults and children with laboratory-confirmed mpox. Patients will be identified following clinical assessment and laboratory confirmation of mpox infection as part of usual clinical care. All eligible and consenting patients will be randomly allocated (1:1) to receive tecovirimat or matching placebo for 14 days, each to be given in addition to the usual standard of care.

Study endpoints: The primary clinical efficacy endpoint is the time to resolution of active lesions. Secondary efficacy endpoints are time to complete lesion resolution, and the time to negative cultures for monkeypox virus in throat and lesion swabs. Safety data will also be collected. For the main analyses, follow-up will be censored at 28 days after randomisation. Additional information on longer term outcomes may be collected through review of medical records or linkage to medical databases (such as those managed by NHS Digital and other health care organisations). Additional assessments may be conducted following the end of the main assessment period of the study (28 days) to assess complete resolution of mpox symptoms.

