2.4 Eligibility

2.4.1 Inclusion criteria

Patients are *eligible* for the study if **all** of the following are true:

- (i) Laboratory-confirmed monkeypox infection
- (ii) The presence of active skin or mucosal lesion(s)^a
- (iii) Patient is appropriate to be managed without hospitalisation
- (iv) For women with reproductive potential,^b willingness to use effective contraception^c from the time of enrolment through study day 28

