2.8 Sample size

For the log-rank test of the primary endpoint ‘time to active lesion resolution’, the two key determinants of power are the total number of active lesion resolution events and the treatment-to-control ratio of the rate of active lesion resolution.

Table 1 displays the power of this test for various scenarios. In total, 318 patients with lesion resolution by day 28 are needed to detect a 40% improvement in the rate of lesion resolution as measured by the rate ratio (akin to a “hazard ratio” but for a positive outcome instead of death; values greater than one indicate improved outcomes) with at least 85% power and a two-sided α of 0.05. Conservatively assuming that the observed event rate of 77% from the 2007-2011 INRB/USAMRIID observational study will apply to the combined time to event data of experimental and control groups yields a total targeted sample size of 413 participants.³ A total sample size of 500 is planned to account for one interim analysis and approximately 10% losses to follow-up.

Table 1. Number of events needed to have 80% and 85% power at $2P=0.05$ to detect an improvement in the primary outcomes.

Rate Ratio	Scenario for 80% Power ($\beta=0.20$)		Scenario for 85% Power ($\beta=0.15$)	
	Number of Events Needed	Number of Patients Needed*	Number of Events Needed	Number of Patients Needed*
1.30	457	594	522	678
1.40	278	362	318	413
1.50	191	249	219	285

* Assumes that 77% of patients will experience the event and does not account for potential dropout. In the 2007-2011 INRB/USAMRIID observational study, 77% of patients reached lesion resolution (as defined above) within 22 days.

Since the event rate is uncertain, the sample size will be reviewed and revised based on blinded data (i.e. with time to event data for the experimental and control groups combined), when about 50% of the originally planned number of participants have reached determination of the primary endpoint.

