2.14 Analysis population

The intention to treat (ITT) population will be all participants randomised, irrespective of treatment received. This ITT population will be used for analysis of efficacy and safety data. For interim analyses, baseline data will be reported for all participants with data available and outcome data will be reported for all participants who have reached day 28 after randomisation.

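### The nearest-value imputation rule has no maximum gap, so stopping reports with active lesions is scored as unresolved to day 28 rather than censored at the last report

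*SAP*

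**What the plan says.** SAP 4.1.1 defines the primary outcome as the first day with no active lesions, "regardless of whether active, unscabbed, lesions are reported on subsequent days". For gaps in the daily record it states: "Missing values for a particular day will be imputed as the reported value taken nearest in time before or afterwards". Ties go to the earlier report. There is no limit on the length of a gap and no separate provision for withdrawal or loss of contact.

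SAP 4.1.2 reuses the rule for complete lesion resolution. SAP 4.1.3 does so for time to sustained absence of analgesia: "Imputation of missing data and the method of time-to-event analysis will be as for the primary outcome above". That outcome is "defined as the first day from which analgesia is consistently not required until day 28".

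The ITT population in SAP 2.14 "will be all participants randomised, irrespective of treatment received". The only censoring point stated is in the protocol summary: "For the main analyses, follow-up will be censored at 28 days after randomisation". The sample size in SAP 2.8 was raised to 500 to "account for one interim analysis and approximately 10% losses to follow-up". SAP 2.11 describes two reporting streams: a daily participant form on days 1 to 28 and weekly staff calls on days 7, 14, 21 and 28. SAP 3.3 reports day-28 completeness descriptively. No sensitivity analysis of the imputation rule is planned.

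**The concern.** After the last report, the nearest reported value is always that last report, so the rule becomes last observation carried forward without limit. Its effect depends on the outcome.

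- **Lesion outcomes.** A last report of active lesions (or of scabs, for complete resolution) keeps the participant in the risk set as a non-event to day 28. A log-rank and Kaplan-Meier analysis would ordinarily censor such a person at last contact.
- **Analgesia.** One analgesia-free report followed by silence is filled as analgesia-free to day 28, so dropout becomes success.
- **Gaps before the first report.** If the first diary entry is on day 6 and says resolved, the event is dated to day 1, or to day 4 if the day-0 assessment counts as a report. The SAP does not say which applies.

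At stake are the primary rate ratio, the Kaplan-Meier curves, power and, if dropout differs by arm, the type I error of the primary test.

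**Working it through.** **The plan's own figure.** For a rate ratio of 1.40, two-sided alpha 0.05 and 85% power, the events needed are 4 × (1.960 + 1.036)² / (ln 1.4)² = 35.91 / 0.1132 = 317.2, so 318. Patients: 318 / 0.77 = 413. Both match SAP Table 1. The sample size is not in error. The question is what the imputation rule does to the analysis.

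**Leading-gap example.** The first diary entry is on day 6 (resolved) and day 0 is counted as active. Days 1 and 2 are nearer to day 0. Day 3 is a tie and takes the earlier value, active. Day 4 is 4 days from day 0 and 2 from day 6, so it is filled as resolved. Without day 0, every day from day 1 is filled as resolved.

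**Simulation inputs.** From protocol 2.4.3: median about day 9 and 77% resolved by day 22. A Weibull placebo curve with S(9) = 0.50 and S(22) = 0.23 has shape ln(ln(1/0.23) / ln 2) / ln(22/9) = 0.841 and scale 9 / (ln 2)^(1/0.841) = 13.92. Day-28 resolution is then about 83.5% on placebo and 92.0% on tecovirimat at a hazard ratio of 1.4. There are 250 participants per arm, event days are rounded up, the log-rank test is unstratified, the rate ratio is exp((O−E)/V), and rejection is at |Z| > 1.98. The share, timing and balance of dropout are assumptions.

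**True hazard ratio 1.4, 10% dropout in each arm:**

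| Dropout pattern | SAP rule: RR, power | Censored at last report: RR, power |
|---|---|---|
| Spread over days 1–27 | 1.41, 91% | 1.43, 92% |
| All in week 1 | 1.38, 87% | 1.43, 93% |
| Resolvers stop the day before healing and answer no later call | 1.33, 76% | 1.43, 92% |

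Full data also give about 1.43, because the O−E estimate sits slightly above 1.40. In the third row, apparent day-28 resolution falls to 0.9 × 83.5% = 75.2% on placebo and 0.9 × 92.0% = 82.8% on tecovirimat.

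**Alternative curve (77% resolved by day 28).** With 10% week-1 dropout in each arm, day-28 resolution falls from 77.0% / 87.2% (placebo / tecovirimat) to 72.5% / 82.6%. Power is 88% under the SAP rule against 91% with censoring. At 20% it is 82% against 89%.

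**Unequal week-1 dropout.** The 15% / 5% split averages 10%, the plan's overall allowance.

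| Placebo / tecovirimat | True HR | RR, SAP rule | RR, censored |
|---|---|---|---|
| 15% / 5% | 1.4 | 1.55–1.58 | 1.43 |
| 5% / 15% | 1.4 | 1.21–1.25 | 1.43 |
| 15% / 5% | 1.0 | 1.11–1.14 | 1.00 |
| 10% / 10% | 1.0 | 1.00 | 1.00 |

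With no effect and the 15% / 5% split, two-sided rejection is about 14% with the day-28 curve and about 21% to 25% with the day-22 curve, depending on when in week 1 reports stop. Censoring gives about 5%. With equal dropout and no effect, the SAP rule rejects in 4.7% of runs.

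**Limit of the alternative.** If 5% on placebo and 15% on tecovirimat stop just before healing, at a true hazard ratio of 1.4, censoring at the last report gives RR 1.27 against about 1.43 with full data. The SAP rule gives about 1.05.

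**The case against.** The strongest reply is that the weekly calls limit the damage. A diary lapse alone leaves a gap of about a week at most. In the stop-before-healing scenario, if 50% of stoppers answer the next call, the SAP rule gives RR 1.37 and power 86%; at 80% it gives 1.40 and 91%; at 90%, 1.42 and 92%. This stands if call data count as reports, which the SAP does not say. It does not help for participants lost to both streams, whom the 10% allowance anticipates.

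A second reply is that 10% loss unrelated to healing costs little, with power staying above the planned 85%. That is correct when dropout is similar in both arms.

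A third is that counting dropout as failure is deliberate conservatism. The SAP does not say so. The analgesia outcome goes the other way, and higher dropout on placebo makes the lesion analysis anti-conservative.

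Finally, censoring at the last report is not a clean remedy: if stopping is related to healing and differs by arm, it too is biased. This stands, and it is why the fix needs wider sensitivity analyses. Analgesia is also only a subsidiary outcome, outside the confirmatory testing sequence.

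**Conclusion.** The concern holds as worded in the heading. The rule as written carries a last active report to day 28, biases lesion-resolution rates down, and credits sustained absence of analgesia to participants who fall silent after one analgesia-free report.

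Three stronger readings are tempting but not supported. A reader might infer that these participants are never censored; the protocol summary censors them at day 28, and the fault is that they are not censored at the last report. A reader might infer that the bias always runs toward 1; that needs a true effect and similar dropout in both arms, and with equal dropout and no effect there is no bias in the rate ratio. A reader might take the fall in power to 76% as the expected loss; it requires 10% of resolvers to stop the day before healing and then miss every call, and nothing in the documents indicates this.

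The more serious exposure is type I error when dropout differs by arm: about 14% to 25% rejection in the assumed example. Blinding makes a large imbalance less likely but does not exclude it. All sizes depend on assumed dropout, because the documents give neither its timing nor its split by arm.

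**What to change.** Amend SAP 4.1.1 to 4.1.3 while still blind to outcomes by arm:

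- (a) Apply nearest-value imputation only to gaps with a report on both sides. Count the day-0 assessment as active (active lesions are an entry requirement) and weekly call data as reports.
- (b) If reports end before resolution, censor at the last report, whether diary or call. Deaths are the exception and stay as non-events to day 28.
- (c) For analgesia, censor participants whose reports end before day 28 at their last report, instead of crediting sustained absence.
- (d) Keep the present rule as a sensitivity analysis. Add one that varies the assumed resolution after dropout separately by arm.

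The cost is SAP wording and a few lines of code, with no new data and no change to the sample size. The primary analysis would then rest on stopping being unrelated to healing given arm; item (d) tests that assumption. The SAP's document history records version 1.0 as preceding unblinded interim monitoring and unblinding of the trial statisticians. The amendment should record its own timing in the same way.

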2.3 Treatment comparisons

Eligible individuals who have provided and consent will be allocated to tecovirimat or placebo using a minimised randomisation program that helps maximise balance between the allocated treatment groups with respect to important prognostic variables (including age [<18 , ≥ 18 - <40 , ≥ 40], sex at birth [male/female], previous orthopoxvirus vaccination [yes/no/not known], severity [localised vs disseminated rash (defined as >1 area, e.g. groin & head)], and days since lesion onset [≤ 7 days or >7 days]).

Randomised participants will be issued with a supply of tecovirimat capsules (200mg) or placebo capsules to be taken orally with food as follows:

- Adults aged 18 years or older: three capsules twice a day for 14 days (total daily tecovirimat dose: 1200 mg)
- Children and adolescents aged <18 years:
 - Estimated body weight ≥ 13 to <25 kg: one capsule twice a day for 14 days (total daily tecovirimat dose: 400 mg).
 - Estimated body weight ≥ 25 to <40 kg: two capsules twice a day for 14 days (total daily tecovirimat dose: 800 mg).
 - Estimated body weight ≥ 40 kg: three capsules twice a day for 14 days (total daily tecovirimat dose: 1200 mg).

Although PK/PD modelling suggest that higher doses may be preferable in adult patients weighing ≥ 120 kg, all adults allocated to active tecovirimat will receive the current standard dose (as above) without adjustment for weight.

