2.5.1 Methods of analysis

Comparisons will be made between all participants randomised to the different treatment arms, irrespective of whether they received their allocated treatment (“intention-to-treat” analyses).

Primary and first secondary outcome: For time-to-event analyses of the primary and first secondary outcome, the tecovirimat group will be compared with the placebo group using a stratified log-rank test (days since symptom onset ≤ 7 , >7 days). Kaplan-Meier estimates for the time to event will also be plotted (with associated log-rank p-values). The log-rank ‘observed minus expected’ statistic (and its variance) will also be used to estimate the average event rate ratio (and its confidence interval) for those allocated to treatment group versus the placebo group.

Other secondary outcomes: Time to consistently negative culture for monkeypox virus on throat swab and on swab of most recent active skin or mucosa lesion at Days 7, 14, 21, and 28 will be analysed using an interval censored Weibull model. A negative culture will be considered ‘consistently negative’ if it is not followed by a positive culture on the same type of swab during subsequent assessments.

Subsidiary and safety outcomes: Clinical status on an ordinal scale will be compared between tecovirimat and placebo groups using a proportional odds model.⁽²³⁾ Howard’s method will be used if the proportional odds assumption is not satisfied.⁽²⁴⁾ Monkeypox virus DNA concentration will be compared between groups using the Wilcoxon rank-sum test. Data on hospital admissions and safety will be analysed using Fisher’s exact test. For time-to-event analyses of the subsidiary outcome of need for analgesia, the tecovirimat group will be compared with the placebo group using a stratified log-rank test (days since lesion onset ≤ 7 , >7 days).

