3.3 Baseline information

After informed consent has been given, a CCO Clinician (doctor or nurse with appropriate training) will record the following information on a web-based form:

- Participant details (name, date of birth, sex at birth, self-reported weight for adults, measured weight for children, NHS/CHI number)
- Medical history (diabetes mellitus, HIV infection, other immunosuppression (e.g. solid organ transplant), known chronic kidney or liver disease)
- Orthopoxvirus vaccination history
- Symptom onset date (fever onset, lesion onset)
- Pregnancy and breastfeeding status (to confirm eligibility)
- Relevant medications (including current use of repaglinide, systemic corticosteroids, HIV medications, immunosuppressants including cancer treatments)
- Clinical signs and symptoms of mpox (e.g. rash, mouth lesions, breathlessness)

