2.9 Randomisation

Eligible individuals who have provided and consent will be allocated to tecovirimat or placebo using a minimised randomisation program that helps maximise balance between the allocated treatment groups with respect to the following prognostic variables:

- Age (<18, ≥18-<40, ≥40)
- Sex at birth (male/female)
- Previous orthopoxvirus vaccination (yes/no/not known)
- Severity of rash (localised vs disseminated, defined as >1 body area affected)
- Days since onset of rash (≤7 days or >7 days)

The implementation of the randomisation procedure will be monitored by the Senior Trials Programmer, and the Trial Steering Committee notified if an error in the randomisation process is identified.

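### The primary log-rank test is stratified on an undefined symptom-onset date and omits rash severity, although allocation is balanced on lesion onset and severity: valid, but less efficient if those factors are prognostic

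*SAP*

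**What the plan says.** **Primary test.** SAP 4.1.1 states that "the tecovirimat group will be compared with the placebo group using a stratified log-rank test (days since symptom onset", split at 7 days. Protocol 2.5.1 uses the same factor for the primary and first secondary outcomes ("compared with the placebo group using a stratified log-rank test (days since symptom onset"). No other stratum or covariate is named. The same log-rank O−E statistic and variance give the rate ratio.

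**Allocation.** Protocol 2.3 minimises on age, sex, vaccination, rash severity and "days since lesion onset", and describes these as important prognostic variables. SAP 2.9 lists "Days since onset of rash" and "Severity of rash (localised vs disseminated, defined as >1 body area affected").

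**Dates recorded.** Protocol 3.3 collects "Symptom onset date (fever onset, lesion onset"), which is one heading with two dates. Neither document says which date defines the stratum.

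**Analgesia outcome.** Protocol 2.5.1 specifies a "stratified log-rank test (days since lesion onset", same cut). SAP 4.1.3 instead refers back to the method for the primary outcome, which means symptom onset.

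**Subgroups.** Protocol 2.5.1 and SAP 4.2 list age, sex, vaccination and time since the first lesion. Severity is not among them. SAP 3.2 reports disseminated infection by arm, as a baseline description only.

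**The concern.** Two separate matters meet in one sentence of the plan.

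The first is definition. If symptom onset means the earlier of fever and rash, the headline test uses a variable that the trial neither balances nor uses for its timing subgroup. If it means lesion onset, the wording is merely loose, but then protocol 2.5.1 uses two terms for one thing. Either way, two recorded dates could supply the stratum for the primary p-value, and the plan does not choose between them.

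The second is efficiency. When allocation balances a prognostic factor and the analysis ignores it, the arms are more alike than the variance formula assumes. The test statistic then varies less than a standard normal under the null, so the test rejects too rarely. The log-rank rate ratio also moves towards 1 relative to the ratio within levels of the factor. The primary test gates all three confirmatory secondary outcomes (protocol 2.5.1, SAP 4.3), so any loss of power carries through to them.

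**Working it through.** **1. The plan's own figure.** Schoenfeld's formula with 1:1 allocation is events = 4(z₁₋α/₂ + z₁₋β)² / (ln RR)². For RR 1.40, two-sided α 0.05 and 85% power this is 4(1.960 + 1.036)² / 0.3365² = 317.2, so 318 events. Then 318/0.77 = 413 patients. Both match Table 1. The formula uses no strata, so these figures are unaffected by the point below.

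**2. When the two dates disagree.** Protocol 1.1 gives a prodrome of generally 1–3 days in most patients. A rash that began 7, 6 or 5 days ago, with a prodrome of 1, 2 or 3 days, puts first symptoms at 8 days: lesion onset is ≤7, symptom onset >7. Under the assumptions in step 3, about 15% of patients fall in different strata. A second simulation (step 5), with a different assumed distribution, gives about 13%.

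**3. Simulation set-up.**
- From the documents: 500 patients, 1:1 allocation, five-factor minimisation, 28 days, 77% event rate (applied in the absence of a treatment effect), 10% dropout, two-sided level 0.0476.
- Assumed, because the documents are silent: 50% disseminated, mean lesion age about 8 days, 0–3 day prodrome, 0.9 biased coin, and all prognostic hazard ratios. Vaccination and age were given smaller effects that grow with the others.

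Check with no prognostic effects: about 396 events arise at RR 1.4. Schoenfeld power is Φ(√(396/4) × 0.3365 − 1.981) = Φ(1.367) = 91.4%. The simulation gave 91.3%.

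**4. Results.** Planned = symptom onset. Fix = lesion onset × severity. All analyses within a row use the same simulated trials.

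| Assumed hazard ratio: severity / lesion onset | Type I error, planned | Type I error, fix | Power at RR 1.4, planned | Power, lesion onset only | Power, fix | Estimated ratio, planned | Estimated ratio, fix |
|---|---|---|---|---|---|---|---|
| 1 / 1 | 4.8% | 4.9% | 91.3% | 91.3% | 90.9% | 1.42 | 1.42 |
| 0.8 / 1.2 | 4.7% | 4.9% | 91.1% | 91.0% | 91.2% | 1.41 | 1.42 |
| 0.7 / 1.3 | 4.2% | 4.6% | 90.3% | 90.7% | 91.4% | 1.41 | 1.42 |
| 0.5 / 1.5 | 3.7% | 4.7% | 86.8% | 87.6% | 90.9% | 1.38 | 1.42 |
| 0.33 / 2 | 2.8% | 5.1% | 79.2% | 82.0% | 90.8% | 1.33 | 1.42 |

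The third and fourth rows use 12,000 replicates and the others 4,000. Monte Carlo error is about 0.2–0.3 points for type I error and 0.3–0.6 for power. The O−E estimate runs slightly above 1.40 even with correct strata, so the ratio columns should be compared with each other.

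The last three rows split as follows:
- Total loss: 91.4 − 90.3 = 1.1 points, 90.9 − 86.8 = 4.1, and 90.8 − 79.2 = 11.6.
- Due to the date alone: 0.4, 0.8 and 2.8 points.
- Due to severity: 0.7, 3.3 and 8.8 points.

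The conservatism follows from the null standard deviation s of Z, since type I error ≈ 2[1 − Φ(1.981/s)]. For the planned test in the fourth row, s = 0.951. Then 1.981/0.951 = 2.083, which gives 3.7%, as simulated.

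**5. Second simulation.** This took hazard ratios of 2.0 (late presentation), 0.6 (disseminated) and 1.3 (vaccinated), with a 1–3 day prodrome in 70%. Power at RR 1.4 was 90% as planned, 92% with lesion onset, and 93% with lesion onset × severity. Type I error was 3.9% as planned and 4.65% with both factors. The null standard deviation of Z was 0.97 with either date and 0.99 once severity was added.

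**The case against.** The strongest reply has four parts.

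- **The terms may be synonyms.** Protocol 3.3 treats lesion onset as one of the symptom-onset dates, and the documents use lesion, rash and symptom loosely. This stands in part. The text is ambiguous, and it is not shown that a different variable was intended. A reader might infer that some 13–15% of patients will be put in the wrong stratum. That holds only if the stratum date includes fever onset, and only under an assumed prodrome and lesion-age distribution. Protocol 1.1 also calls the current outbreak clinically atypical.
- **The minimisation factors are not all ignored.** This stands. Age, sex and vaccination are pre-specified subgroups for the primary outcome. Only severity is missing from every comparative analysis.
- **The plan is valid.** This stands. A reader might infer that the false-positive rate is inflated or the estimate biased. The simulated type I error of the planned test is at or below nominal. The SAP names an average rate ratio, and a value nearer 1 than the ratio within severity groups reflects non-collapsibility, not an error.
- **Design power is met.** This largely stands. Planned power exceeds 85% at RR 1.4 in every scenario but the strongest. Part of that margin comes from about 395 simulated events against the 318 required.

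None of this explains why severity is used to allocate but not to analyse, or removes the conflict on the analgesia outcome.

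**Conclusion.** The point holds as a matter of definition and efficiency. Three textual facts need no assumptions: the stratum date is undefined and differs in name from the allocation and subgroup variable; protocol and SAP conflict on the analgesia outcome; and severity is in no comparative analysis.

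The cost does rest on assumptions. At rate ratio 1.4 the power loss is nil if the factors are not prognostic, about 1 point with modest effects (severity 0.7, lesion onset 1.3), about 4 points with stronger ones (0.5, 1.5) and about 12 points at the extreme (0.33, 2). Omitting severity causes most of it; the date mismatch alone costs 0.4 to 2.8 points in those three scenarios. The documents do not support a reading that the trial is underpowered or its primary test unsound. The change should be made because it is nearly free and removes an analyst's choice from the primary p-value.

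**What to change.** In SAP 4.1.1, and by reference in 4.1.2 for complete lesion resolution and 4.1.3 for analgesia, and in protocol 2.5.1, stratify the log-rank test and its O−E rate ratio on days since lesion onset (≤7, >7) by rash severity (localised, disseminated). State that both are taken as recorded at minimisation. Use one term for the date throughout; this also settles the analgesia conflict.

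Do not stratify on every minimisation factor. Adding vaccination and age to the strata lowered simulated power from 91.4% to 89.2% and from 90.9% to 88.4% in the third and fourth scenarios, through sparse strata. A Cox model adjusted for the minimisation factors may be added, as a supportive analysis only.

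The cost is wording in two documents. Both variables are needed to allocate treatment, so nothing new is collected. If the factors prove not to be prognostic, the simulated power cost is 0.4 points (91.3% to 90.9%), within Monte Carlo error. Make the change before unblinding, including the unblinded interim assessment of benefit. The only SAP version in its document history is marked as preceding both.
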